#### For durvalumab treatment

- Patients may delay dosing under certain circumstances.
  - Dosing may be delayed per the Dosing Modification and Toxicity Management Guidelines (see [Section 8.4.5.1](#)) due to either an immune or a non-immune-related adverse event (AE).
  - If dosing must be delayed for reasons other than treatment-related toxicity, dosing will resume as soon as feasible (see [Section 8.4.5.1](#)).
  - One cycle is equal to 28 days.
  - Dosing intervals of subsequent cycles may be shortened as clinically feasible in order to gradually align treatment cycles with the schedule of tumor efficacy (RECIST 1.1) and PRO assessments. Time between 2 consecutive doses cannot be less than 21 days, based on the half-life of durvalumab (see the current Investigator's Brochure for durvalumab).

### **For olaparib/placebo treatment**

- Patients may delay and subsequently resume dosing per standard clinical practice. Dose reductions may also occur if the study treatment dose is not tolerable (see Section [8.4.5.2](#)).
  - If dosing must be delayed for reasons other than treatment-related toxicity, dosing will occur as soon as feasible.
  - One cycle is equal to 28 days (56 doses of olaparib/placebo administered twice daily [BID]).

**Table 1 Schedule of assessments for patients who are receiving study treatment**

	Screening	C1 a	C2 a	C3 a	C4 a	C5 to PD a,b	EOT visit c	For details, see Section	
Week	-4 to -1	0	q4w ±3 days unless dosing needs to be held for toxicity reasons						
Day	-28 to -1	1	q28days ±3 days unless dosing needs to be held for toxicity reasons						
Informed consent									
Informed consent: study procedures	X							5.1	
Informed consent: genetic sample and analysis (optional)	X							5.1	
Randomizationd	X							4.1, 6.4	
Study procedures									
Physical examination (full)	X							8.2.2	
Targeted physical examination (based on symptoms)		X	X	X	X	X	X	8.2.2	
Vital signs	X	X e	X e	X e	X e	X e	X e	8.2.3	
Weight	X	X	X	X	X	X	X	8.2.3	
ECG f,g	X	As clinically indicated						8.2.4	
Concomitant medications	<----->							6.6	
Demography, including baseline characteristics and tobacco use	X							5.1, 5.2	
Eligibility criteria h	X							5.1, 5.2	
TNM staging	X							5.1	
Laboratory assessments									
HBsAg, HCV antibodies, and HIV antibodies	X							8.2.1	
Clinical chemistry	X	X i	Prior to each durvalumab administration j				X	Table 9	
Hematology	X	X i	Prior to each durvalumab administration j				X	Table 10	
Coagulation parameters (aPTT and INR)	X	As clinically indicated						Table 10	
TSH (reflex free T3 or free T4 k )	X	X i	X	X	X	X	X	Table 9	
Urinalysis g,l	X	As clinically indicated						Table 11	
Pregnancy test m	X	As clinically indicated						5.1	

**Table 1 Schedule of assessments for patients who are receiving study treatment**

	Screening	C1 a	C2 a	C3 a	C4 a	C5 to PD a,b	EOT visit c	For details, see Section	
Week	-4 to -1	0	q4w ±3 days unless dosing needs to be held for toxicity reasons						
Day	-28 to -1	1	q28days ±3 days unless dosing needs to be held for toxicity reasons						
Pharmacokinetics									
Durvalumab PK sample (serum)		X n	X o		X o			8.5.1.1	
Olaparib PK sample (plasma)		X o	X o		X o			8.5.1.2	
Monitoring									
WHO/ECOG performance status	X	X	X	X	X	X	X	8.2.5	
AE/SAE assessment p	<----->								8.3
Drug accountability		X	All visits						6.3
IP administration									
Durvalumab q		X r	X r	X r	X r	X r		6.1.1.1	
Olaparib/placebo q		X	X	X	X	X		6.1.1.2	
Other assessments and assays									
Tumor biopsy (FFPE sample) s	X s					X s		8.1.2, 8.8.1.1	
Genetic sample	X							8.7, Appendix D	
Durvalumab immunogenicity assessment (ADA sampling to identify ADA responses in patient circulation)		X o	X o		X o			8.5.2	
Whole blood for gene expression (PaxGene-RNA tubes)	X o	X o	X o			X o		8.8.1.2	
Whole blood – exploratory analysis (mandatory) t	X	X	X	X	X	X	X	8.8.1.3	
Urine (mutational analysis)	X	X	X	X	X	X	X	8.8.1.4	
ctDNA (plasma)	X	X	X	X	X	X	X	8.8.1.5	
EORTC QLQ-C30 and EQ-5D-5L u		X	q4w (±7 days relative to Cycle 1 Dose 1 date) until treatment discontinuation						8.1.4.1, 8.1.4.2

**Table 1 Schedule of assessments for patients who are receiving study treatment**

	Screening	C1 a	C2 a	C3 a	C4 a	C5 to PD a, b	EOT visit c	For details, see Section
Week	-4 to -1	0	q4w ±3 days unless dosing needs to be held for toxicity reasons					
Day	-28 to -1	1	q28days ±3 days unless dosing needs to be held for toxicity reasons					
PGIC u				X	q8w (±7 days relative to the date of Cycle 1 Dose 1 date) until treatment discontinuation			8.1.4.3
VES-13 u		X						8.2.6
Efficacy evaluations								
Tumor assessment (CT or MRI) (RECIST 1.1) b	X	q8w ±1 week beginning 8 weeks after randomization for the first 48 weeks, and then q12w ±1 week thereafter (relative to the date of randomization) until clinical progression with or without RECIST 1.1-defined radiological progression. An additional follow-up scan is requested, if clinically feasible. The schedule of q8w ±1 week for the first 48 weeks and then q12w ±1 week thereafter MUST be followed regardless of any delays in dosing.						8.1

a These cycles refer to the 28-day cycles of administration of durvalumab.

b Screening/Baseline scans and tumor assessments by RECIST 1.1 criteria should be performed no more than 28 days before the date of randomization and, ideally, should be performed as close as possible to and prior to the date of randomization. Patients will have on-study scans done q8w ±1 week for the first 48 weeks relative to the date of randomization and then q12w ±1 week thereafter until clinical progression with or without RECIST 1.1-defined radiological progression. An additional follow-up scan is requested, if clinically feasible and if criteria for treatment beyond progression are met. Clinically stable patients with RECIST 1.1-defined radiological PD who continue to receive study treatment at the discretion of the Investigator and patient should receive a subsequent scan, preferably at the next regularly scheduled imaging visit but no earlier than 4 weeks later, and this subsequent scan is assessed using the Confirmation of Radiological Progression criteria described in [Appendix F](#). RECIST 1.1 assessments will be performed on images from CT (preferred) or MRI, each preferably with IV contrast of the chest, abdomen, and pelvis. Additional anatomy should be imaged based on signs and symptoms of individual patients at baseline and follow-up. If an unscheduled assessment was performed and the patient has not progressed, every attempt should be made to perform the subsequent assessment at their next scheduled visit.

c EOT will occur when both IPs are discontinued.

d It is recommended that patients commence study treatment as soon as possible after randomization, and ideally within 3 days.

e On the first infusion day, patients in the durvalumab + olaparib and durvalumab + placebo groups will be monitored, and vital signs will be collected/recorded in the eCRF prior to, during, and after infusion of IP. BP and pulse will be collected from patients before, during, and after each infusion and at the following times (based on a 60-minute infusion): prior to the beginning of the infusion (measured once from approximately 30 minutes before up to 0 minute [ie, the beginning of the infusion]), approximately 30 minutes during the infusion (halfway through infusion), and at the end of the infusion (approximately 60 minutes ±5 minutes). For subsequent infusions, BP, pulse, and other vital signs should be measured and collected/recorded in the eCRF prior to the start of the infusion.

f Any clinically significant abnormalities detected require triplicate ECG results.

g Individual sites are required to indicate in the unscheduled visit eCRF if an ECG or a urinalysis was performed during study treatment.

- h Eligibility should be confirmed prior to randomization.
- i If screening laboratory assessments are performed within 3 days prior to Day 1 (first infusion day), they do not need to be repeated at Day 1. Serum or plasma chemistry (serum sample is preferred), hematology, and/or LFT monitoring may be performed more frequently if clinically indicated.
- j Chemistry/hematology parameters should be collected at any time during the cycle visit for subjects that have discontinued durvalumab due to toxicity.
- k Free T3 or free T4 will only be measured if TSH is abnormal or if there is clinical suspicion of an AE related to the endocrine system.
- l Site to specify type of test used and provide appropriate lab reference range. Preferred method is Urine Dipstick.
- m For women of childbearing potential only. A urine or serum pregnancy test is acceptable. Women of childbearing potential are required to have a pregnancy test within 7 days prior to the first dose of the IP (ie, durvalumab, olaparib, or placebo) and then every 4 weeks. Pregnancy test may occur on Day 1, but results must be available and reviewed by the treating physician or Investigator prior to commencing an infusion
- n Within 10 minutes of the end of infusion.
- o Samples should be taken pre-dose for both olaparib and durvalumab.
- p For AEs/SAEs reported during screening, additional information such as medical history and concomitant medications may be needed.
- q Treatment to be administered until confirmed PD.
- r Results for LFTs, electrolytes, and creatinine must be available before commencing an infusion (within 3 days) and reviewed by the treating physician or Investigator prior to dosing.
- s Archival tumor is mandatory for enrollment; biopsies at progression are optional, and the treating physician will judge the feasibility of such a procedure.
- t Whole blood for exploratory analyses will be collected during screening, pre-dose on Day 1 of Cycles 1 to 4, every 12 weeks thereafter (ie, every 3 cycles), at discontinuation/progression, and at the 90-day follow-up visit ([Table 2](#)).
- u PRO assessments will be done using a site-based electronic device at the beginning of the dosing cycle regardless of dosing delays. In case of dose delay, PROs may also be assessed during all ad hoc unscheduled visits. It is preferred that PRO questionnaires are completed prior to any other study procedures (following informed consent) and before discussion of disease progression to avoid biasing the patient's responses to the questions.

Note: All assessments on treatment days are to be performed prior to infusion, unless otherwise indicated.

ADA Antidrug antibody; AE Adverse event; aPTT Activated partial thromboplastin time; BP blood pressure; C Cycle; CR Complete response; CT Computerized tomography; ECG Electrocardiogram; ECOG Eastern Cooperative Oncology Group; eCRF Electronic case report form; EDTA Ethylenediaminetetraacetic acid; EORTC QLQ-C30 European Organisation for Research and Treatment of Cancer 30-item core quality of life questionnaire; EOT End of treatment; EQ-5D-5L EuroQoL 5-dimension, 5-level health state utility index; FFPE Formalin-fixed paraffin-embedded; HBV Hepatitis B virus; HCV Hepatitis C virus; HIV Human immunodeficiency virus; IM Intramuscular; IO Immuno-oncology; IP Investigational product; INR International normalized ratio; IV Intravenous; LFT Liver function test; MRI Magnetic resonance imaging; PD Progressive disease; PGIC Patient Global Impression of Change; PK Pharmacokinetic(s); PR Partial response; PRO Patient-reported outcome; q4w Every 4 weeks; q8w Every 8 weeks; q12w Every 12 weeks; q28days Every 28 days; RECIST 1.1 Response Evaluation Criteria in Solid Tumors, version 1.1; SAE Serious adverse event; T3 Triiodothyronine; T4 Thyroxine; TNM Classification of Malignant Tumors (Tumor, Lymph Nodes, Metastasis); TSH Thyroid stimulating hormone; VES-13 Vulnerability Elders Survey-13; WHO World Health Organization.

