### **Follow-up of patients post discontinuation of study drug**

Patients who have discontinued treatment due to toxicity or symptomatic deterioration, clinical progression, or who have commenced subsequent anticancer therapy will be followed up with tumor assessments until RECIST 1.1-defined PD plus an additional follow-up scan or until death (whichever comes first) and followed up for survival.

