### **7.1.1 Procedures for discontinuation of study treatment**

Discontinuation of study treatment, for any reason, does not impact the patient's participation in the study. A patient who decides to discontinue IP will always be asked about the reason(s) for discontinuation and the presence of any AE. The patient should continue attending subsequent study visits, and data collection should continue according to the study protocol. If the patient does not agree to continue in-person study visits, a modified follow-up must be arranged to ensure the collection of endpoints and safety information. This follow-up could be a telephone contact with the patient, a contact with a relative or treating physician, or information from medical records. The approach taken should be recorded in the medical records. A patient that agrees to modified follow-up is not considered to have withdrawn consent or to have withdrawn from the study.

Patients who are permanently discontinued from further receipt of the IP, regardless of the reason, will be identified as having permanently discontinued treatment. Patients who are permanently discontinued will enter follow-up (see [Table 2](#)). Patients who permanently discontinue 1 IP due to toxicity but continue the other IP will continue all treatment assessments (see [Table 1](#)).

Patients who permanently discontinue IP for reasons other than RECIST 1.1-defined disease progression should continue to have RECIST 1.1 scans performed q8w  $\pm$ 1 week beginning 8 weeks after randomization for the first 48 weeks (relative to the date of randomization), and then every 12 weeks (q12w)  $\pm$ 1 week thereafter until clinical progression with or without RECIST 1.1-defined radiological PD plus an additional follow-up scan (if criteria for treatment beyond progression are met) or death (whichever comes first) as defined in [Table 2](#).

If a patient is discontinued for RECIST 1.1-defined progression, then the patient should have 1 additional follow-up scan performed preferably at the next (and no later than the next) scheduled imaging visit, and no less than 4 weeks after the prior assessment of PD.

All patients will be followed for survival until the end of the study.

Patients who decline to return to the site for evaluations should be contacted by telephone as indicated in [Table 2](#) as an alternative.

Patients who have permanently discontinued from further receipt of the IP will need to be discontinued from the IVRS/IWRS.

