## 8.1 Efficacy assessments

This study will evaluate the primary endpoint of PFS. Secondary endpoints include DoR, ORR, OS, OS18, and PFS6. Efficacy assessments of PFS, PFS6, DoR, and ORR will be derived (by AstraZeneca) using Investigator assessments according to RECIST 1.1.

Tumor assessments utilize images from CT (preferred) or MRI, each preferably with IV contrast, of the chest, abdomen, and pelvis, collected during screening/baseline and at regular (follow-up) intervals during study treatment. Any other areas of disease involvement should be additionally imaged based on the signs and symptoms of individual patients.

The RECIST 1.1 guidelines ([Appendix F](#)) provide a method of assessment of change in tumor burden in response to treatment. Screening/Baseline imaging should be performed no more than 28 days before start of study treatment, and ideally should be performed as close as possible to and prior to the start of study treatment. The RECIST 1.1 assessments of baseline images identify TLs (defined measurable) and non-target lesion (NTLs). On-study images are evaluated for TLs and NTLs chosen at baseline and for new lesions when they appear. This allows determination of follow-up TL response, NTL response, and overall timepoint tumor responses (CR, PR, SD, PD, or not evaluable [NE]).

Radiologic efficacy for all patients (both treatment arms) will be assessed on images collected q8w  $\pm$ 1 week for the first 48 weeks relative to the date of randomization and q12w  $\pm$ 1 week thereafter until RECIST 1.1-defined objective disease progression or off-study. The assessment schedule must be followed regardless of any delays in dosing (refer to [Table 1](#)). If an unscheduled assessment is performed and the patient has not progressed, every attempt should be made to perform the subsequent assessments at his/her next regularly scheduled imaging visit. Assessments of tumor response (CR, PR, or SD) must be confirmed at the next (and no later than the next) scheduled imaging visit, and no less than 4 weeks and no more than 8 weeks after the prior assessment.

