### **Progression-free survival**

PFS (per RECIST 1.1 as assessed by the site Investigator) will be defined as the time from the date of randomization until the date of objective disease progression or death (by any cause in the absence of progression) regardless of whether the patient withdraws from therapy or receives another anticancer therapy prior to progression (ie, date of event or censoring – date of randomization + 1). Patients who have not progressed or died at the time of analysis will be censored at the time of the latest date of assessment from their last evaluable RECIST 1.1 assessment. However, if the patient progresses or dies after 2 or more consecutive missed visits, the patient will be censored at the time of the latest evaluable RECIST 1.1 assessment prior to the 2 missed visits. If the patient has no evaluable visits or does not have baseline data, they will be censored at Day 1 unless they die within 2 visits of baseline; then they will be treated as an event with date of death as the event date.

The PFS time will always be derived based on scan/assessment dates and not visit dates.

RECIST 1.1 assessments/scans contributing toward a particular visit may be performed on different dates. The following rules will be applied:

- For Investigator assessments, the date of progression will be determined based on the earliest of the RECIST 1.1 assessment/scan dates of the component that indicates progression.

- When censoring a patient for PFS, the patient will be censored at the latest of the scan dates contributing to a particular overall visit assessment.

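### Two conflicting rules for when tumour scans stop put the primary PFS endpoint at risk of informative censoring

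*Protocol*

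**What the plan says.** The protocol states the end of scanning in two ways.

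**Rule A, stop at clinical progression.** The tumour-assessment rows of Table 1 and Table 2 (Section 1.1), with footnotes b and j, schedule scans "until clinical progression with or without RECIST 1.1-defined radiological progression". Section 7.1.1, for patients who stop treatment for reasons other than RECIST progression, says "until clinical progression with or without RECIST 1.1-defined radiological PD plus an additional follow-up scan". Both tables and footnote j ask for one more scan where clinically feasible. Footnote b narrows that request: "An additional follow-up scan is requested, if clinically feasible and if criteria for treatment beyond progression are met". Section 7.1.1 ties the extra scan to the same criteria.

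**Rule B, continue to RECIST progression.** The synopsis paragraph on follow-up after study drug covers patients who stopped for toxicity, symptomatic deterioration or clinical progression, and those who started other anticancer therapy. It says they "will be followed up with tumor assessments until RECIST 1.1-defined PD plus an additional follow-up scan or until death". Section 8.1 has all patients in both arms scanned "until RECIST 1.1-defined objective disease progression or off-study".

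**Endpoint.** Section 9.4.1.1 starts PFS at randomization and counts it "until the date of objective disease progression or death (by any cause in the absence of progression) regardless of whether the patient withdraws from therapy". Patients without an event are censored at their last evaluable RECIST assessment. Progression or death after two or more consecutive missed visits is censored back to the last evaluable assessment before them. Appendix F says symptomatic deterioration is a reason to stop therapy and does not describe an objective response.

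**The concern.** Clinical progression is not a PFS event, but under Rule A it can end the scans that would document one. The patients affected are those who appear about to fail, so censoring them at the previous scan is related to outcome.

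Two things are at stake. If the arms lose such patients equally, the trial collects events more slowly. If they lose them unequally, the primary hazard ratio is biased. Scans not taken cannot be reconstructed at analysis, so the point has to be settled in the assessment schedule.

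**Working it through.** **1. The plan's own figure.** Inputs from Section 9.2: HR 0.55, two-sided 5%, 90% power, 1:1, 75 per arm. Schoenfeld events = 4(1.96 + 1.2816)² / (ln 0.55)² = 42.03 / 0.3574 = 117.6, so 118. Maturity is 118/150 = 79%. The planned event count reproduces, and this point does not change it.

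**2. Path of a patient with clinical-only progression.**
- Section 7.1 requires both drugs to stop, so the patient moves to Table 2 and Section 7.1.1.
- Section 7.1.1 continues scans until clinical progression, which has already happened. Under Rule A no further scheduled scan is due.
- The extra scan is only requested. Where it depends on the treatment-beyond-progression criteria (footnote b, Section 7.1.1), Appendix F requires the absence of clinically significant progression with declining performance status, which such patients would generally not meet.
- PFS is then censored at the last evaluable scan, unless the patient dies before two missed visits.
- Under Rule B the same patient keeps being scanned and contributes an event at RECIST progression or death.

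**3. How far deaths can fill the gap.** Section 9.2 expects about 44 deaths in total at the cutoff for 118 PFS events. At least 118 − 44 = 74 PFS events must therefore be progressions. Most of the primary endpoint depends on scans.

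**4. What the attrition analysis recovers (Section 9.4.2.1).** It restores actual event times observed after two or more non-evaluable assessments, so late deaths return. It does not restore scans never taken or count clinical progression as an event, and within the same analysis it adds censoring at subsequent therapy.

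**5. Illustrative size.** From the protocol: control median PFS 3 months, 6-month accrual, scans every 8 weeks, cutoff at 118 events. Assumed: uniform accrual, exponential times, median post-progression survival of 9 months, and the share of patients with clinical-only progression. Such patients are censored at the last scan unless they die before the second missed one. No follow-up scan is credited.

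| True HR | Share, control / experimental | Result with cutoff at 118 events |
|---|---|---|
| 0.55 | 0% / 0% | power about 89%, cutoff near month 13 |
| 0.55 | 15% / 15% | power about 90%, cutoff near month 18 |
| 0.55 | 20% / 10% | power about 80% (0.80 to 0.82 in repeat runs) |
| 1.0 | 10% / 20% | favourable false positives about 5-6%, against 2.5% nominal |

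The bias can run either way. In a simpler simulation with a fixed cutoff 7 months after the last patient and no later deaths counted (so an upper end), a true HR of 0.55 appears as 0.59 with 20% / 10% and 0.49 with 10% / 20%. A true HR of 1.0 appears as 1.08 and 0.92.

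**6. Ceiling.** If a share x of the 150 patients can never contribute an event, at most 150(1 − x) events are available. Reaching 118 needs x ≤ 32/150 = 21%.

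**The case against.** The strongest reply is that this is an inconsistency of wording whose effect depends on what sites do. The tumour-assessment rows in both tables refer to Section 8.1 for details, and Section 8.1 has Rule B. The extra scan would document progression in some patients. The trial is double-blind, which limits differential calling of clinical progression. The reversed-indicator Kaplan-Meier plot of time to censoring would help expose an imbalance.

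Much of that stands, and it rules out several stronger readings:

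- A reader might infer that the primary endpoint is informatively censored as a matter of fact. The documents show conflicting instructions, with no share of affected patients and no account of site practice. They support a risk only.
- A reader might infer a certain loss of events and power by fixing the cutoff at month 13. Section 9.2 ties the cutoff to about 118 events; the 7 months after last recruitment is an estimate. Equal shares therefore cost time, with little or no power.
- A reader might infer that olaparib toxicity makes the shares unequal. Appendix F keeps patients who stop for toxicity without radiographic progression on the original imaging schedule, and no document supports an imbalance in either direction.

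The reply does not remove the conflict. Section 8 makes adherence to the schedule of activities essential, so a site following the tables would be complying. The extra scan is not mandatory, and the diagnostics can reveal missing scans but not replace them.

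**Conclusion.** The contradiction is established from the current text alone. Rule A stands in five places, and Rule B in the synopsis and Section 8.1. Rule B is the one that fits the PFS definition. The consequence is a risk of informative censoring, confined to patients whose scans stop at clinical-only progression and who do not die before two missed visits.

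Its size cannot be fixed from the documents. At an assumed 15% in both arms the main cost is a cutoff about 5 months later. With assumed imbalances of 10 percentage points, power falls to about 80% in one direction, and the favourable false-positive rate rises to about 5-6% in the other. These figures rest on assumed shares and an assumed 9-month post-progression survival, and any follow-up scans actually obtained would reduce them. The planned 118 events and 90% power are correct and stay as they are.

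**What to change.** Reconcile five places to the rule already in the synopsis and Section 8.1: Table 1, Table 2, footnote b, footnote j and Section 7.1.1. In each, state that scans continue on the randomization-based schedule until RECIST 1.1-defined progression plus the follow-up scan, death or withdrawal of consent, whatever the reason for stopping treatment, and including after clinical progression or new anticancer therapy.

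The change concerns endpoint collection only and leaves the treatment-stopping rules as they are. It costs an amendment of wording and a few extra scheduled scans in patients with clinical-only progression, which the synopsis already requires. A supplementary analysis counting clinical progression as a PFS event would help show how much the gap mattered, but does not replace the scans.

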#### For both treatment arms

- Patient-reported outcome (PRO) assessments will be done at the beginning of the dosing cycle regardless of dosing delays. In case of dose delay, PRO assessments may also be assessed during all ad hoc unscheduled visits. Tumor efficacy (Response Evaluation Criteria in Solid Tumors, version 1.1 [RECIST 1.1]) assessment dates are not affected by dose delays and remain as originally scheduled, as they are based on the date of randomization (not the date of therapy).
- All other scheduled assessments must be performed relative to the start of the dosing cycle such that all laboratory procedures, etc., required for dosing should be performed within 3 days prior to dosing.

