### **8.2.1 Clinical safety laboratory assessments**

Blood and urine samples for determination of clinical chemistry, hematology, and urinalysis will be taken at the times indicated in the assessment schedules and as clinically indicated (see [Table 1](#) and [Table 2](#)).

Clinical laboratory safety tests, including serum pregnancy tests, will be performed in a licensed clinical laboratory according to local standard procedures. Sample tubes and sample sizes may vary depending on the laboratory method used and the routine practice at the site. Urine pregnancy tests may be performed at the site using a licensed test (urine or serum pregnancy test). Abnormal clinically significant laboratory results should be repeated as soon as possible (preferably within 24 to 48 hours).

Additional safety samples may be collected if clinically indicated at the discretion of the Investigator. The date, time of collection, and results (values, units, and reference ranges) will be recorded on the appropriate eCRF.

The Investigator should make an assessment of the available results with regard to clinically relevant abnormalities. The laboratory results should be signed and dated and retained at the site as source data for laboratory variables.

For information on how AEs based on laboratory tests should be recorded and reported, see Section 8.3.7.

The laboratory variables measured are presented in Table 9 (clinical chemistry), Table 10 (hematology), and Table 11 (urinalysis).

Other safety tests to be performed at screening include assessment for HBsAg, HCV antibodies, and HIV antibodies.

The following laboratory variables will be measured:

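### From Cycle 2, blood counts and chemistry are tied to durvalumab infusions, and footnote j of Table 1 detaches them only when durvalumab is discontinued, not when it is delayed while olaparib/placebo continues

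*Protocol*

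**What the plan says.** **Schedule.** In Table 1 (Section 1.1), the clinical chemistry and hematology rows from Cycle 2 onward read "Prior to each durvalumab administration", followed by a sample at the end-of-treatment visit. Footnote a says of the cycle columns: "These cycles refer to the 28-day cycles of administration of durvalumab". The table heading sets four-weekly visits within 3 days but makes an exception when dosing is held for toxicity.

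**Effect of a delay.** The rules for both arms in Section 1.1 keep tumor scans on dates counted from randomization and keep patient-reported outcomes going regardless of dosing delays. The rest moves with dosing: "All other scheduled assessments must be performed relative to the start of the dosing cycle such that all laboratory procedures" and similar procedures "required for dosing should be performed within 3 days prior to dosing".

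**Exceptions.** Footnote j: "Chemistry/hematology parameters should be collected at any time during the cycle visit for subjects that have discontinued durvalumab due to toxicity". Section 7.1.1: "Patients who permanently discontinue 1 IP due to toxicity but continue the other IP will continue all treatment assessments". Both concern durvalumab, or one of the two products, having been stopped.

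**The other permitted state.** Section 6.7.1 permits durvalumab dose delays. Section 8.4.5 names discontinuation and delay together and says that olaparib/placebo may go on in either case.

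**What remains during a delay.** Footnote i: "hematology, and/or LFT monitoring may be performed more frequently if clinically indicated". Section 8.2.1: "Additional safety samples may be collected if clinically indicated at the discretion of the Investigator".

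**The concern.** Footnote j shows that the protocol's authors saw that samples tied to infusions lapse when infusions cease. It deals with one of the two states that Section 8.4.5 names and leaves out the other. A site that follows Table 1 exactly can therefore keep a patient on twice-daily olaparib/placebo during a durvalumab delay with no scheduled count.

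Olaparib is the product for which counts matter most. Section 2.3.3.2 lists anemia, neutropenia, lymphopenia and thrombocytopenia among its effects. The actions in Tables 12 and 13 start from a hemoglobin value or a graded count, so an asymptomatic fall triggers nothing until blood is drawn. The weekly counts in Section 8.4.5.2 begin only after hematological toxicity is already known and prolonged.

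At stake is the timeliness of dose interruption and reduction for individual patients, not the efficacy comparison.

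**Working it through.** The protocol states no figure for this interval, so there is none to reproduce. The check is a comparison of the rules, followed by simple arithmetic on the interval between scheduled counts.

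**1. Which rule applies in each state, with olaparib/placebo continuing**

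| Durvalumab status | Rule for counts and chemistry | Scheduled? |
|---|---|---|
| Given as planned | Table 1 rows, before each infusion | Yes, about every 28 days |
| Discontinued for toxicity | Footnote j and Section 7.1.1 | Yes, at the cycle visit |
| Delayed | Table 1 rows, waiting for the next infusion | Not until durvalumab resumes |

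**2. Inputs**
- Normal interval: 28 days (Section 1.1, Table 1).
- Samples due within 3 days before dosing (Section 1.1).
- 56 olaparib/placebo doses per 28 days, that is, 2 per day (Section 1.1).
- Delay *D*: the protocol gives no maximum, so 14, 28, 42 and 56 days are assumptions used to show the range.

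**3. Interval between scheduled counts**

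Case A, the usual one: samples were drawn before the planned infusion and the hold was then decided. Interval ≈ *D* (±3 days for the pre-dose window). Excess over normal = max(0, *D* − 28).

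Case B, less usual: the hold was decided before any sample was drawn, so the last sample belongs to the previous infusion. Interval ≈ 28 + *D*. Excess = *D*.

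| *D* (assumed, days) | Case A interval | Case A excess | Case B interval | Case B excess |
|---|---|---|---|---|
| 14 | 14 | 0 | 42 | 14 |
| 28 | 28 | 0 | 56 | 28 |
| 42 | 42 | 14 | 70 | 42 |
| 56 | 56 | 28 | 84 | 56 |

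**4. Doses between counts** = 2 × interval. A 42-day interval covers 2 × 42 = 84 doses and a 56-day interval 2 × 56 = 112, against 56 normally.

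**5. Would an existing attendance serve as the anchor?** EORTC QLQ-C30 and EQ-5D-5L are due every 4 weeks, ±7 days, counted from the first dose. Two consecutive attendances could therefore lie up to 28 + 7 + 7 = 42 days apart. Tablets are dispensed at Table 1 visits (Section 6.1.1.2), whose four-weekly timing is relaxed during a toxicity hold, and the overage in each container is not quantified. Neither attendance guarantees a 28-day interval, so a fixed interval from the last sample is the safer rule. With ±3 days it gives 25 to 31 days.

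**The case against.** The case against giving this much weight is a good one, and most of it stands.

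- **In the usual case nothing is lost for delays up to 28 days.** Samples normally precede the decision to hold. This stands, and it limits the size of the point.
- **The state is narrow.** Grade 3 or 4 events considered related to study treatment also interrupt it (Section 8.4.5.2), and delays for reasons other than toxicity are to end as soon as feasible. What remains is mainly lower-grade holds, or toxicity not attributed to olaparib/placebo. This stands.
- **Such patients are already under attention.** Section 8.4.5 asks for thorough evaluation, Section 8.2.1 for prompt repetition of abnormal results, and extra samples are allowed. This is true, but these provisions respond to a known problem or leave the draw to judgment. They do not schedule a count for a patient who feels well.
- **The durvalumab toxicity guidelines may set monitoring during a hold.** Section 8.4.5.1 refers to them as a separate document, not shown here. This cannot be excluded. It is still better that Table 1 itself carries the routine counts needed for olaparib.
- **A delayed patient keeps an anchor, the resumed infusion.** This explains why footnote j speaks only of discontinuation. But the anchor has no stated latest date.

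A reader might infer that the protocol leaves these patients unmonitored, or that gaps of 42 to 84 days are to be expected. The document supports neither. Counts are permitted at any time. The longer intervals need either a delay beyond 28 days or a missed pre-hold sample, together with a site that draws nothing at its discretion.

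**Conclusion.** The gap is real but small. During a durvalumab delay with olaparib/placebo continuing, the protocol schedules no hematology or chemistry until durvalumab resumes, although it makes provision for the parallel case of discontinuation. If samples were taken before the hold, the interval is longer than normal only when the delay exceeds 28 days: by 14 days at an assumed 42-day delay and by 28 days at 56. If no sample was taken before the hold, any delay lengthens it.

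This rests on reading Table 1 cycles as durvalumab cycles, as footnote a states, and on assumed delays. How often such delays occur, and in how many patients, cannot be estimated from the protocol. The unseen toxicity guidelines could reduce the gap further. There is no effect on endpoints, alpha or power. It is a cheap improvement for patient safety, not a flaw in the design.

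**What to change.** Reword footnote j of Table 1 along these lines:

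> For subjects in whom durvalumab is delayed or discontinued while olaparib/placebo continues, collect chemistry/hematology every 28 days (±3 days) from the last sample for as long as olaparib/placebo is taken, combined where possible with the q4w PRO or tablet-dispensing attendance. A sample already drawn for a held or resumed infusion within that window need not be repeated.

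The cost is one footnote, a few extra routine draws at the normal four-weekly frequency, and occasionally an additional visit where questionnaire or dispensing attendance falls outside the window.
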